Title: Porcine Xenograft versus Second Intention Healing: A randomized, evaluator-blinded clinical trial

NCT Number: 03931746

Document Date: September 16, 2019

Porcine Xenograft versus Second Intention Healing: A randomized, evaluator-blinded clinical trial

Protocol Number: 18-0715

National Clinical Trial (NCT) Identified Number: 03931746 Principal Investigator: [name] Sponsor: Investigator Initiated

Affected Section(s)	Summary of Revisions Made	Rationale
6.5.1	We have added a description of the "rescue therapy" that may be provided if a patient's wound has not healed at approximately 10 to 12 weeks following the surgical date. This section was previously left blank.	While typical healing time is within 12 weeks of the surgical date, it is standard of care to provide the rescue therapy at approximately 10 to 12 weeks if a patient's wound is not healing normally. Furthermore, it is not possible to assess the primary outcome (POSAS observer total score) if the wound has not healed.
9.3	We have added a sentence to this section to clarify that patients who receive the rescue therapy will be included in the Modified Intention-to-Treat Population.	We plan to analyze the data according to the treatment to which a patient was randomized. This will provide an accurate estimate of the treatment effect in the setting of actual clinical practice. Furthermore, given that typical healing time is within 12 weeks, we do not expect a large number of patients to require rescue therapy. Accordingly, the effect of the rescue therapy on treatment effect estimates would be minimal.

Summary of Changes from Previous Version:

Table of Contents

STATE	EMENT OF COMPLIANCE	1
1	PROTOCOL SUMMARY	1
1.1	Synopsis	1
1.2	Schema	2
1.3	Schedule of Activities (SoA)	4
2	INTRODUCTION	4
2.1	Study Rationale	4
2.2	Background	4
2.3	Risk/Benefit Assessment	5
2.	.3.1 Known Potential Risks	5
2.	.3.2 Known Potential Benefits	6
2.	.3.3 Assessment of Potential Risks and Benefits	6
3	OBJECTIVES AND ENDPOINTS	6
4	STUDY DESIGN	10
4.1	Overall Design	10
4.2	Scientific Rationale for Study Design	11
4.3	Justification for Dose	11
4.4	End of Study Definition	12
5	STUDY POPULATION	12
5.1	Exclusion Criteria	12
5.2	Lifestyle Considerations	12
5.3	Screen Failures	12
5.4	Strategies for Recruitment and Retention	12
6	STUDY INTERVENTION	13
6.1	Study Intervention(s) Administration	13
6.	.1.1 Study Intervention Description	13
6.	.1.2 Dosing and Administration	13
6.2	Preparation/Handling/Storage/Accountability	13

(1) The trial will be conducted in accordance with International Conference on Harmonisation Good Clinical Practice (ICH GCP), and applicable United States (US) Code of Federal Regulations (CFR). The Principal Investigator will assure that no deviation from, or changes to the protocol will take place without prior documented approval from the Institutional Review Board (IRB), except where necessary to eliminate an immediate hazard(s) to the trial participants. All personnel involved in the conduct of this study have completed Human Subjects Protection and ICH GCP Training.

The protocol, informed consent form(s), recruitment materials, and all participant materials will be submitted to the IRB for review and approval. Approval of both the protocol and the consent form must be obtained before any participant is enrolled. Any amendment to the protocol will require review and approval by the IRB before the changes are implemented to the study. All changes to the consent form will be IRB approved; a determination will be made regarding whether a new consent needs to be obtained from participants who provided consent, using a previously approved consent form.

1 PROTOCOL SUMMARY

1.1 SYNOPSIS

Title:	Porcine Xenograft versus Second Intention Healing: A randomized, evaluator-blinded clinical trial
Study Description: Objectives:	A comparison of porcine xenograft placement to second intent healing will be performed. Upon completion of dermatologic surgery following standard procedures, patients will be randomized into one of two groups (porcine xenograft placement or second intention healing). Weekly follow- up via questionnaires will be conducted as well as a final office visit follow- up at 3 months. Our study will allow surgeons to make informed decisions on whether porcine xenograft dressing is superior to that of second intention healing and thus worth considering.
	Primary Objective: To compare overall scar quality and aesthetic outcome following second intention healing or porcine xenograft dressing of surgical wounds on the lower extremities.
	Secondary Objective: To compare patients' assessment of scar quality, healing time, scar size, pain level, and complication rates following second intention healing or porcine xenograft dressing of surgical wounds on the lower extremities.
Endpoints:	Detailed descriptions of the endpoints below are included in the body of the protocol.

	Primary Endpoint:
	 POSAS observer scale total score Secondary Endpoints: POSAS patient scale total score Healing time Ratio of scare size to initial defect size Pain score at 1 week following surgery Number of weeks with pain score above 1
	Safety Endpoints: 1. Infection
	2. Bleeding
Study Population:	3. Pain A total of 50 patients, over 18 years of age, post-operative defects greater than 8 mm (in greatest diameter or length of circular or oval geometric shape) on the lower extremities (including the feet), single defect
Phase:	Device study (porcine xenograft)
Description of	The two study sites are Dermatology Practices associated with Northwell
Sites/Facilities Enrolling	Health. Northwell Health Physician Partners Division of Dermatology 1991
Participants:	[name] and [name]
Description of Study	Patients will either be randomized to receive a porcine xenograft or
Intervention:	randomized to allow the wound to granulate via second intention.
Study Duration:	A total of 24 months.
Participant Duration:	The study participants will present to the clinic for their initial surgery and then at the 3-month (\pm 1 month) for wound check and photograph of the wound.

1.2 SCHEMA

1.3 SCHEDULE OF ACTIVITIES (SOA)

Procedures	Screening	Enrollment/Surgery Visit 1	3-Month after surgery- Weekly Questionnaires	3 month follow-up visit ±1 month after surgery date
Informed consent	Х			
Demographics	Х			
Medical history	Х			
Randomization	Х			
Administer study intervention		Х		
Physical exam (including height and weight)	х	Х		х
Vital signs	Х	Х		Х
Height	Х	Х		Х
Weight	Х	Х		Х
Performance status	Х	Х		Х
Hematology				
serum chemistry ^a				
Pregnancy test ^b				
EKG (as indicated)				
Adverse event review and evaluation	Х			
Complete Case Report Forms (CRFs)	х	Х	Х	х
Questionnaire reporting			Х	
Blinded Wound/Scar Assessment				х

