Block randomization will be used to ensure balance in the number of patients allocated to each treatment group. The randomization schedule will be uploaded to REDCap by a statistician outside of the study team. The PI, who will screen eligible subjects, will not have user rights for the Randomization Setup module within REDCap, and will thus be blinded to which treatment arm is next on the randomization list. Due to the nature of the treatment, it will not be possible to blind the patients. Patients will be asked not to inform the blinded physician observers which treatment they received. The PI will use the "Randomize" button within REDCap to assign patients to porcine xenograft or second intention healing after they have been consented and enrolled in the study.

Prior to intervention the defect size will be measured in terms of length and width using a sterile ruler.

After procedure completion wound care instruction will include daily dressing changes and application of petroleum jelly using a cotton tipped applicator to the wound daily until it is healed.

Weekly questionnaires will be given to the patients by phone or email follow-up. All complications and adverse events would be monitored and recorded for both study groups. Assessment of the scar will be blinded in nature.

The mode of treatment for participants will remain consistent throughout the 3-month period, as both methods are reliable for this type of defect. It is not general practice to place a xenograft on a wound healing by second intention or to remove a xenograft after one has been placed to switch to second intention. Should there be any complications, a modified intention to treat principle, described in Section 9, will be adhered to.

The scars for both study groups will be measured at a single follow up visit after 3 months \pm 1 month, and two blinded investigators will then assess the scar for the primary efficacy endpoint at this time. The blinded evaluators will be other MDs not involved in the study who are working in the dermatology department. The Principle Investigator will speak with the physician to outline what needs to be recorded for each patient. The validated physician observer scar assessment instrument (POSAS) will be used for this purpose. Scar size will consist of a length x width measurement using a ruler.

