5 STUDY POPULATION

- Over 18 years of age
- Able to give informed consent themselves
- Willing to return for follow-up visits
- Post-operative defects greater than 8 mm (in greatest diameter or length of circular or oval geometric shape) on the lower extremities (including the feet)
- Single defect

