5.1 EXCLUSION CRITERIA

- Mentally handicapped
- Unable to understand written and oral English
- Incarceration
- Under 18 years of age
- Unwilling to return for follow-up
- Pregnant women
- Wounds less than 8 mm in length
- Wounds on the head, neck or digits
- Patients in which primary linear closure is recommended

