6.3 MEASURES TO MINIMIZE BIAS: RANDOMIZATION AND BLINDING

A randomization schedule will be generated by the Biostatistics Unit at the Feinstein Institute for Medical Research to assign a repair method (porcine xenograft placement or second intention healing). Block randomization will be used to ensure balance in the number of patients allocated to each treatment group. The allocation ratio will be 1:1. The randomization schedule will be uploaded to REDCap by a statistician outside of the study team. The PI, who will screen eligible subjects, will not have user rights for the Randomization Setup module within REDCap, and will thus be blinded to which treatment arm is next on the randomization list. The PI will use the "Randomize" button within REDCap to assign patients to porcine xenograft or second intention healing as they are enrolled.

There will be one physician who will perform all of the surgical procedures, which will remove bias in technique. There will additionally be two blinded physicians who will be tasked with observing the scar and assessing the primary efficacy endpoint (POSAS observer scale total score). The study statistician will be blinded to the treatment groups in order to avoid bias or the appearance of bias. All data provided to the statistician will list the treatment group as "A" or "B".

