9.3 POPULATIONS FOR ANALYSES

A modified intention to treat analysis will be performed. All patients will be analyzed according to randomized treatment assignment, unless a patient prefers an alternative treatment method between the time he/she is randomized and the procedure (in which case the patient will be excluded from the study). The **Modified Intention-to-Treat (mITT) Population** will consist of all patients who receive the study intervention and show up for the 3-month office visit follow-up, during which the primary endpoint is evaluated. The Modified Intention-to Treat Population will also include patients who required the rescue therapy, and had the primary endpoint assessed at a follow-up visit when the wound had completely healed. This population will be used to analyze the primary endpoint and all secondary endpoints.

The **Safety Population** will consist of all patients who receive the randomized study intervention. This population will be used to analyze all safety endpoints.

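### The plan contradicts itself on when patients are randomised; if the Schedule of Activities is followed, post-operative eligibility is settled after the arm is known

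*Combined protocol and SAP*

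**What the plan says.** **Timing of randomisation.** The plan gives three accounts.

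- Section 1.3: the row "Randomization" has one tick, under Screening, alongside consent, demographics and medical history. Nothing is ticked under Enrollment/Surgery Visit 1, where the intervention is given.
- Sections 1.1 and 2.2, in the same words: "Upon completion of dermatologic surgery following standard procedures, patients will be randomized into one of two groups".
- Sections 4.1 and 6.3: the PI presses the REDCap button "after they have been consented and enrolled in the study" (4.1), or uses it "to assign patients to porcine xenograft or second intention healing as they are enrolled" (6.3). Neither section mentions the end of surgery.

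**Eligibility.** Section 5 requires "Post-operative defects greater than 8 mm". Section 5.1 excludes "Patients in which primary linear closure is recommended", without saying when that is judged.

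**Analysis populations.** Section 9.3 defines the mITT population as "all patients who receive the study intervention and show up for the 3-month office visit follow-up", and adds rescued patients who are assessed once healed. The Safety Population requires receipt of the randomised intervention. The only exclusion stated between randomisation and the procedure is a patient's preference for another treatment.

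**The concern.** Concealment in REDCap protects the next assignment until the button is pressed. It cannot protect an eligibility decision made afterwards. The PI screens and randomises (6.3), and one physician performs all the surgery and applies the healing method (10.1.7), so must know the arm to deliver it. Patients are not blinded either (4.1). If allocation came first, a borderline judgement about the wound could differ by arm, and the arms being compared could then differ for a reason other than treatment. The direction cannot be foretold. It depends on which arm loses patients and on how those patients' scars would have scored.

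**Working it through.** **1. What is known at each time point**

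| Criterion | Known at Screening? | Known once surgery is complete? |
|---|---|---|
| Defect above 8 mm (Section 5) | No; it is explicitly post-operative | Yes |
| Linear closure not recommended (5.1) | Not stated; 4.1 links closure partly to anatomical site, which is known beforehand, and partly to small post-operative defects | Yes |

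Under 1.1 and 2.2, both criteria can be checked before allocation. Under 1.3, defect size cannot, and closure perhaps cannot.

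**2. What happens to a patient found ineligible after allocation**

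- Wound closed linearly: the patient receives neither study option, so is in neither the mITT nor the Safety Population under 9.3.
- Wound too small: no rule is given. Section 5.3 (Screen Failures) says only that patients qualify for the device or do not.

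**3. The plan's own sample size (9.2)**

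Inputs: difference 6, SD 6.5, two-sided alpha 0.05, power 80%, efficiency floor 0.864, attrition 10%.

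- Per arm, normal approximation: 2 × (1.960 + 0.842)² × 6.5² / 6² = 18.4, rounded up to 19, so 38 in total. (An exact t-test calculation gives 20 per arm, a trivial difference.)
- 38 / 0.864 = 43.98, so 44.
- 44 / 0.90 = 48.9, so 49. The plan takes 50, which gives 25 per arm.

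The stated 38, 44 and 50 reproduce.

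**4. Room for further losses**

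50 × 0.90 = 45, against 44 needed. One patient is spare.

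The documents give no rate of post-operative ineligibility. The rates below are assumptions, used only to show how quickly the margin goes. Remaining = 50 × (1 − rate) × 0.90. Power is for a t-test on remaining × 0.864 patients in total.

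| Assumed rate | Remaining | Remaining × 0.864 | Power |
|---|---|---|---|
| 0% | 45.0 | 38.9 | 80.0% |
| 5% | 42.75 | 36.9 | 77.9% |
| 10% | 40.5 | 35.0 | 75.5% |
| 20% | 36.0 | 31.1 | 70.1% |

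The factor 0.864 is the plan's worst case for the Mann-Whitney test, so these powers are on the low side. No figure can be put on the bias itself.

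**The case against.** The strongest reply is that the Screening tick is simply misplaced. Sections 1.1 and 2.2 put randomisation after surgery outright. Section 4.1 speaks of surgical defects as what is eligible for enrolment, and the schedule's own surgery column carries the word Enrollment, so the wording of 4.1 and 6.3 fits that visit better than Screening. Section 5.4 says that many patients have consultation and surgery on the same day. The schedule also errs elsewhere: it ticks adverse event review only at Screening, whereas 8.3.4 asks for it at each study visit.

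Most of this stands, and it rules out several stronger readings that a reader might infer:

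- *That the plan is to allocate before surgery.* One table cell says so and two sections say otherwise. What is shown is a contradiction. The reference in 9.3 to a gap between randomisation and the procedure does not settle it, because the term is undefined and 2.3.1 uses it in a way that includes applying the graft.
- *That both criteria can be judged only after surgery.* This is certain for defect size. For linear closure no time of judgement is stated.
- *That the plan removes ineligible patients after allocation.* No sentence says so. It follows from the definitions in 9.3 only for a patient who does not receive the intervention.
- *That the documents imply a particular loss of patients or shift in mean score.* They contain nothing from which to estimate either.

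The reply does not remove the point. Section 4.4 defines participant completion and end of study by the schedule, so it is a working part of the protocol. Same-day surgery shortens the interval but does not fix the order. Sections 4.1 and 6.3, where staff would look for the rule, do not state it.

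**Conclusion.** The contradiction over the timing of randomisation is established from the text. The selection risk is conditional: it arises if a site follows 1.3 rather than 1.1 and 2.2. In that case the defect-size criterion, and possibly the linear-closure exclusion, would be settled with the arm known, and patients who then did not receive the intervention would be lost to both populations in 9.3. The size of the effect is unknown. The sample size calculation stands, with a margin of one patient after the planned attrition. The conclusion does not depend on whether the PI is also the surgeon, which the text with names removed does not show. The point should be corrected because it concerns the allocation step of an open-label, single-surgeon trial and the repair is nearly free.

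**What to change.** 1. In 1.3, move the Randomization tick from Screening to Enrollment/Surgery Visit 1.
2. In 4.1 and 6.3, in line with 1.1 and 2.2, state: *The Randomize button is pressed only after surgery is complete, the defect has been measured, and all Section 5 and 5.1 criteria, including the closure decision, have been recorded in REDCap.*
3. Keep consent before surgery. In 5.3, class consented patients who fail the post-operative criteria as screen failures, not counted in the 50.
4. In 9.3, say whether the procedure means the surgery or the repair, and report by arm anyone found ineligible after randomisation.

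Cost: one table cell, a few sentences and an eligibility check ahead of the REDCap button. Some consented patients will become screen failures. The sample size does not change, and no closure rule is altered; only the time at which the decision is recorded is fixed.

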2 INTRODUCTION

2.1 STUDY RATIONALE

There is no clear evidence to indicate whether porcine xenograft placement is more beneficial for wound healing following dermatologic surgery (Mohs surgery or excision surgery) versus allowing the wound to heal on its own. We will perform a comparison of porcine xenograft placement to second intent healing.

2.2 BACKGROUND

Porcine xenograft has been used as a barrier to the skin for over 30 years, and due to its wound healing promoting factors, we believe that its use may result in decreased healing time, smaller scar size, better cosmetic outcomes, lower pain levels, and decreased rates of infection and other post-surgical complications.

Upon completion of dermatologic surgery following standard procedures, patients will be randomized into one of two groups (porcine xenograft placement or second intention healing). Weekly follow-up via questionnaires will be conducted as well as a final office visit follow-up at 3 months.

The application of porcine xenograft dressings for wound healing was first studied in 1985, with evidence supporting several benefits when compared to traditional dressings [1]. Subsequent studies have substantiated the use of this dressing for a variety of clinical settings [2,3].

The EZ-DERM[™] porcine xenograft is a biosynthetic dressing made from porcine collagen containing aldehyde crosslinking [1,3]. It has been most commonly applied to the management of 2nd degree burns, both partial-thickness and full-thickness defects [4]. This dressing can be used for two healing purposes, either for primary healing or as an intermediate in the preparation for a skin graft [2].

Compared to other biosynthetic dressings, porcine xenografts afford longer wound adherence and can be stored at room temperature [1]. The xenograft triggers rejection by the surgical defect, increasing local vascularization [5]. It also allows for rapid granulation, a reduced risk of infection, as well as reduced wound-related fluid and thermal losses [6-8]. There is also evidence that the quicker wound healing reduces the frequency of dressings, hospitalization time, pain, and analgesic [9,10].

Several clinical case series have extended the use of porcine xenografts to Mohs Micrographic Surgery (MMS) to facilitate post-operative wound care. Porcine xenograft dressings were determined to be safe, well-tolerated, and able to be applied to a wide anatomical range [3, 11,12].

In addition to biosynthetic dressings, healing via second intention remains an alternative [13,14]. The extremities of elderly patients are a common location for wound granulation. Drawbacks to second intention healing on the extremities include prolonged healing time and extended wound care for the patient [15].

Chern et. al. completed a review of biological dressings in dermatologic surgery and concluded that there is a limited number of studies focusing on the conclusive benefits of dressings [16]. Although studies have established that EZ-DERM[™] was helpful for wound healing following Mohs surgery, there have not been any definitive statistical measures reported in the literature. Additionally, there is a lack of studies assessing the direct comparison to second intention healing.

Our plan is to perform a direct comparison of porcine xenograft placement to second intent healing. Based on the previously studied benefits of the xenograft as a barrier to the skin and one which has wound healing promoting factors, we believe that its use may result in decreased healing time, smaller scar size, better cosmetic outcomes, lower pain levels, and decreased rates of infection and other postsurgical complications.

Our study will allow surgeons to make informed decisions on whether porcine xenograft dressing is superior to that of second intention healing and thus worth considering.

2.3 RISK/BENEFIT ASSESSMENT

2.3.1 KNOWN POTENTIAL RISKS

Second intention Healing:

Risk of infection, bleeding, scarring, numbness

Xenograft Placement:

Localized skin allergy: EZ-DERM Porcine Xenograft is latex-friendly and non-cytotoxic. Risk of slightly longer procedure: Application of the xenograft may increase the length of the procedure by up to 10 minutes. Risks of infection, bleeding, scarring, and numbness. Rates of infection followed skin surgery are less than 1%.

For Both:

Risk of Randomization: Your group might receive a less effective treatment and/or have more side effects than the other treatment group(s).

Risk of loss of confidentiality: There is a possibility that documents will be seen by individuals not included in this study. However, patient data will be stored in a password-protected electronic data capture tool in order to reduce the risk of loss of confidentiality.

